# Staggered enrolment in PoP epochs (for details see Section 5.2 and Figure 6 and Figure 8):

In a first step (PoP step 1) first dose of vaccination will be performed with a staggered approach. Enrolment will be stopped as soon as 40 subjects have been vaccinated with the first dose of the GSK *S. aureus* candidate vaccine or placebo. Only subjects who already signed the ICF and entered the screening phase, at the time of enrolment hold, will be allowed to continue the study; therefore, approximately 40 subjects (30 subjects receiving GSK *S. aureus* candidate vaccine and 10 receiving placebo) will be evaluated for safety. After iSRC evaluation of unblinded safety data collected up to the Day 8 after first dose (including laboratory assessments) for the last vaccinated subject of this staggered subset (step 1) has shown lack of safety issues, the PoP step 2, (full enrolment of the remaining subjects in the PoP epochs) will continue.

The investigator will not be permitted to start the administration of the second vaccine/placebo dose in the staggered PoP subset from step 1 (approximately 40 subjects) until receipt of the favourable outcome of the SRT and iSRC Chair, which needs to evaluate all the safety data available up to Day 68 (including laboratory assessments) related to the subjects of the fourth group (Full dose adjuvanted) of the last dose-escalation safety lead-in step. Conditionally, unblinded data may be evaluated by iSRC and, only after positive opinion of iSRC, the next step (i.e. second dose of staggered PoP subset) can be started.

All subjects will be closely observed at the site for a minimum of 60 minutes after vaccination. Occurrence of solicited AEs within 30 minutes post vaccination observation must be recorded in the CRF (Table 4).

For both, the dose-escalation safety lead-in and PoP, the investigator is not permitted to start the administration of Dose 1 for the next group until receipt of the favourable outcome of the safety assessment committees evaluation (SRT/iSRC), documented and provided in writing (scanned and emailed), authorising the investigator to proceed (Figure 7 and Figure 8). The same applies for the administration of Dose 2 in the fourth group of the dose-escalation safety lead-in and for the administration of Dose 2 in the staggered enrolment of first 40 subjects of the PoP epoch.

In case more than 1 subject is to be vaccinated on the same day per site, subjects should be vaccinated sequentially at this site and at least 60 minutes apart as acute adverse reactions, like anaphylactic shock, typically occur within 1 hour of vaccination (for holding rules refer to Section 8.6.3 and Table 26). Therefore, not vaccinating subjects in parallel and leaving at least 60 minutes between vaccinations of 2 consecutive subjects will ensure that, in the event of an acute adverse reaction, the site will be able to provide the required medical attention. The 2 sentinel subjects of Groups 1 to 4 of dose-escalation safety lead-in should be vaccinated on 2 different days.

\* Safety reviews will take into account all safety data accumulated up to the specified timepoint

\* All safety reviews (i.e. SRTs/iSRCs) will take into account all safety data accumulated up to the specified timepoint

#### 8.6.2. Outcome of safety evaluation

- If no safety signal is observed, the favourable outcome of the safety evaluations will be documented and provided in writing (scanned and e-mailed), authorising the investigator to start vaccination of subjects with the subsequent dose as well as enrolment and vaccination of the remaining subjects in the next step of the study, as applicable.
- In case the investigator becomes aware of holding rule(s) 1 is met, he/she should immediately inform GSK of the event (Refer to Table 24 for contact information).
- If a safety signal is observed during the safety evaluations or if any of the holding rules 2a-c is met, the iSRC Chair (or his/her representative) is responsible for the urgent communication to GSK, including the rationale for the decision to put the vaccination on hold or not.
- All site staff will be informed about that final decision (suspend or continue the study) by their local GSK contact. CRDL who is the primary contact will inform the local GSK contact.

#### 8.6.3. Study holding rules

The safety holding rules are defined in Table 26. Holding rules 1 will be assessed by the investigator on a continuous basis irrespective of the number of subjects enrolled and meeting any of these holding rules will trigger a hold of vaccination irrespective of number of subjects enrolled and/or timing of the event relative to vaccination. Holding rules 2 will be assessed by the iSRC during the safety evaluations on unblinded data. Please refer to Appendix 7, Section 12.7 for the definition of the Toxicity Grading Scale for Healthy Adult and Adolescent Volunteers Enrolled in Preventive Vaccine Clinical Trials.

These holding rules have been written under the assumption that the safety data from all subjects will be available. If the data from all subjects are not available (i.e. in case a subject is lost to follow-up), then the holding rules will be assessed on a pro-rata basis.

Of note, no formal holding rules will be applied for other safety data such as non-lifethreatening SAEs, missed visits due to vaccine-related AEs, Grade 1 and Grade 2 (Refer to Section 12.5.8.2.2) solicited and unsolicited AEs in the 7-day follow-up period and unsolicited AEs collected from Day 8 to Day 30 after vaccination. However, these data, if available, will also be reviewed by the safety assessment committee (SRT/iSRC as applicable) in order to allow for an overall assessment of the benefit/risk ratio of vaccination.

| Holding
rule | Event   | FTIH Dose-
escalation
Safety Lead-In
steps 1-4
Number of
subjects
needed to
trigger the
hold | Staggered
enrolment step of
PoP vaccination
epoch (PoP step
1)
Number and % of
subjects needed
to trigger the hold | Full enrolment
step of PoP
vaccination
epoch (PoP
step 2)
Number of
subjects
needed to
trigger the hold |
|-----------------|---|--|---|---|
| 1a              | Death or any life-threatening SAE   | ≥1   | ≥1  | ≥1  |
| 1b              | Any withdrawal from the study (by
investigator or subject request) following a
Grade 3 AE that cannot reasonably be
attributed to a cause other than vaccination   | ≥1   | ≥1  | N/A   |
| 1c              | Any local or general solicited AE leading to
hospitalization, or fever >40°C (104°F) or
necrosis at the injection site, within the 7-
day (Days 1-7) post-vaccination period   | ≥1   | ≥1  | N/A   |
| 2a              | Any Grade 3 solicited local AE (lasting 48h
or more) in an investigational group, within
the 7-day (Day 1-7) post-vaccination period  | ≥1   | ≥ 6/30 or 20%   | N/A   |
| 2b              | Any Grade 3 solicited general AE (lasting
48h or more) in an investigational group,
within the 7-day (Day 1-7) post-vaccination
period   | ≥1   | ≥ 6/30 or 20%   | N/A   |
| 2c              | Any Grade 3 unsolicited AE in an
investigational group, that cannot
reasonably be attributed to a cause other
than vaccination, within the 7-day (Day 1-7)
post-vaccination period or any Grade 3
abnormality in pre-specified haematological
or biochemical laboratory parameters in an
investigational group within the 7-day (Day
1-7) post-vaccination period * | ≥1   | ≥ 6/30 or 20%   | N/A   |

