# Figure 9 Evaluations based on 6 subjects per group – Risk assessment curve for 1 formulation based on the proposed safety holding rules (dose-escalation safety lead-in steps)

The Figure 9 illustrates that, with 6 subjects per study group:

• Each holding rule 1a-c and 2a-c has more than 82% chance of being met for vaccination with a true incidence rate above 25% and has more than 53% chance of not being met for vaccination with a true incidence rate below 10%.

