# Figure 10 Evaluations based on 30 subjects per group – Risk assessment curve for 1 formulation based on the proposed safety holding rules (staggered step)

The Figure 10 illustrates that, with 30 subjects per study group:

- Each holding rule 1a-c has more than 78% chance of being met for vaccination with a true incidence rate above 5% and has more than 74% chance of not being met for vaccination with a true incidence rate below 1%.
- Each holding rule 2a-c has more than 80% chance of being met for vaccination with a true incidence rate above 25% and more than 93% chance of not being met for vaccination with a true incidence rate below 10%.

Safety holding rule after 200, 250, 300, 350 subjects

The Figure 11 illustrates that, with 200-350 subjects per study group:

The holding rule 1a has a chance ranging from 3% (with 350 subjects) to 13% (with 200 subjects) of not being met for vaccination with a true incidence rate below 1% and has more than 98% chance of being met for vaccination with a true incidence rate above 2%.

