# 12.5.2. Definition of SAE

A SAE is any untoward medical occurrence that:

- a. Results in death,
- b. Is life-threatening,

Note: The term 'life-threatening' in the definition of 'serious' refers to an event in which the subject was at risk of death at the time of the event. It does not refer to an event, which hypothetically might have caused death, had it been more severe.

c. Requires hospitalisation or prolongation of existing hospitalisation,

Note: In general, hospitalisation signifies that the subject has been admitted at the hospital or emergency ward for observation and/or treatment that would not have been appropriate in the physician's office or in an out-patient setting. Complications that occur during hospitalisation are also considered AEs. If a complication prolongs hospitalisation or fulfils any other serious criteria, the event will also be considered serious. When in doubt as to whether 'hospitalisation' occurred, or was necessary, the AE should be considered serious.

Hospitalisation for elective treatment of a pre-existing condition (known or diagnosed prior to informed consent signature) that did not worsen from baseline is NOT considered an AE.

d. Results in disability/incapacity, OR

Note: The term disability means a substantial disruption of a person's ability to conduct normal life functions. This definition is not intended to include experiences of relatively minor medical significance such as uncomplicated headache, nausea, vomiting, diarrhoea, influenza like illness, and accidental trauma (e.g. sprained ankle) which may interfere or prevent everyday life functions but do not constitute a substantial disruption.

- e. Is a congenital anomaly/birth defect in the offspring of a study subject.
- f. Grade 4 laboratory abnormalities (Refer to Appendix 7, Section 12.7).

Medical or scientific judgement should be exercised in deciding whether reporting is appropriate in other situations, such as important medical events that may not be immediately life-threatening or result in death or hospitalisation but may jeopardise the subject or may require medical or surgical intervention to prevent one of the other outcomes listed in the above definition. These should also be considered serious. Examples of such events are invasive or malignant cancers, intensive treatment in an emergency room or at home for allergic bronchospasm, blood dyscrasias or convulsions that do not result in hospitalisation.

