# Table 36FDA toxicity grading scales for hematology/ biochemistry
parameters evaluated in the current study

| Serum *  | Mild
(Grade 1)  | Moderate
(Grade 2) | Severe
(Grade 3) | Potentially Life
Threatening
(Grade 4)** |
|--|--------------------|-----------------------|---------------------|--|
| Creatinine – mg/dL                                   | 1.5 – 1.7          | 1.8 – 2.0             | 2.1 – 2.5           | > 2.5 or requires
dialysis                  |
| Liver Function Tests –ALT, AST
increase by factor | 1.1 – 2.5 x
ULN | 2.6 – 5.0 x
ULN    | 5.1 – 10 x ULN      | > 10 x ULN                                     |

\* The laboratory values provided in the tables serve as guidelines and are dependent upon institutional normal parameters. Institutional normal reference ranges should be provided to demonstrate that they are appropriate. \*\* The clinical signs or symptoms associated with laboratory abnormalities might result in characterization of the laboratory abnormalities as Potentially Life-Threatening (Grade 4). For example, a low sodium value that falls within a Grade 3 parameter (125-129 mE/L) should be recorded as a Grade 4 hyponatremia event if the subject had a new seizure associated with the low sodium value.

\*\*\* "ULN" is the upper limit of the normal range.

| Homotology *                        | Mild          | Moderate      | Severe     | Potentially Life-Threatening |
|-------------------------------------|---------------|---------------|------------|------------------------------|
| Heinatology                         | (Grade 1)     | (Grade 2)     | (Grade 3)  | (Grade 4)                    |
| Hemoglobin (Female) - gm/dL         | 11.0 – 12.0   | 9.5 – 10.9    | 8.0 – 9.4  | < 8.0                        |
| Hemoglobin (Female)                 | Any decrease  | 1.6 – 2.0     | 2.1 – 5.0  | > 5.0                        |
| change from baseline value -        | – 1.5         |               |            |                              |
| gm/dL                               |               |               |            |                              |
| Hemoglobin (Male) - gm/dL           | 12.5 – 13.5   | 10.5 – 12.4   | 8.5 – 10.4 | < 8.5                        |
| Hemoglobin (Male)                   | Any decrease  | 1.6 – 2.0     | 2.1 – 5.0  | > 5.0                        |
| change from baseline value –        | – 1.5         |               |            |                              |

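### The laboratory limb of holding rule 2c counts Grade 3 only, so a Grade 4 value without actual risk of death does not count through that limb

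*Protocol*

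**What the plan says.** Rule 2c in Table 26 has two limbs. The first covers Grade 3 unsolicited AEs with no reasonable cause other than vaccination. The second covers pre-specified haematology and biochemistry values and is worded "post-vaccination period or any Grade 3" abnormality. The threshold is at least 1 subject in each lead-in step and at least 6/30 (20%) in PoP Step 1. The rule does not apply in Step 2. The Table 26 footnote grades laboratory values on the FDA scale in Section 12.7. In Table 36, ALT or AST at 5.1 to 10 x ULN is Grade 3 and above 10 x ULN is Grade 4.

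Section 8.6.3 adds: "Holding rules 2 will be assessed by the iSRC during the safety evaluations on unblinded data". It also says: "Of note, no formal holding rules will be applied for other safety data such as non-lifethreatening SAEs".

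Section 12.5.2 lists life-threatening events as SAE criterion (b) and requires risk of death at the time: "It does not refer to an event, which hypothetically might have caused death, had it been more severe". Laboratory values have their own criterion: "f. Grade 4 laboratory abnormalities (Refer to Appendix 7, Section 12.7".

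Section 8.6.4 gives the chance of meeting the rules. For the lead-in: "Each holding rule 1a-c and 2a-c has more than 82% chance of being met for vaccination with a true incidence rate above 25" per cent. For Step 1: "Each holding rule 2a-c has more than 80% chance of being met for vaccination with a true incidence rate above 25" per cent.

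**The concern.** Solicited and unsolicited AEs are graded up to 3 (Section 12.5.8.2.2), so in rules 2a and 2b and in the first limb of 2c, Grade 3 is the worst grade. Only the laboratory limb uses a four-grade scale, and there the same phrase leaves the worst grade out. This looks like a drafting slip, although the protocol does not say so.

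At stake is the ordering of a stated threshold in a first-in-human study. As written, the threshold can be harder to reach when the toxicity is worse, and whether a Grade 4 value meets any formal rule depends on who reads the text.

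**Working it through.** **1. Can a Grade 4 value meet a formal rule by another route?** Take a vaccinee with ALT above 10 x ULN, no symptoms, and no other Grade 3 value.

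- *Laboratory limb of 2c.* It names Grade 3. Nothing in Table 26, its footnote or Section 12.7 adds Grade 4. Not met as worded.
- *First limb of 2c.* Severe intensity in 12.5.8.2.2 is functional: the event stops everyday activities. An asymptomatic value does not plainly qualify, but the investigator grades by clinical judgement, so this is arguable.
- *Rule 1a.* It needs death or a life-threatening SAE. Section 12.5.2 ties that term to actual risk of death and lists Grade 4 laboratory values separately, under (f). If every Grade 4 value were life-threatening under (b), item (f) would add nothing. Against that, Table 36 heads the Grade 4 column as potentially life-threatening, and its footnote says clinical signs "might result in characterization of the laboratory abnormalities as Potentially Life-Threatening (Grade 4"). Arguable, but not clear.
- *Remaining text.* If the SAE is not life-threatening, 8.6.3 says that no formal holding rule applies.

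**2. Counts under the two wordings** (laboratory limb only)

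| Situation | As written | 'Grade 3 or higher' |
|---|---|---|
| Lead-in group, one Grade 3 | 1, met | 1, met |
| Lead-in group, one Grade 4 only | 0, not met | 1, met |
| Step 1, six at Grade 3 | 6/30, met | 6/30, met |
| Step 1, five at Grade 3 and one at Grade 4 only | 5/30, not met | 6/30, met |

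This ordering needs no assumption about rates.

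**3. The plan's own figures.** With independent vaccinees and X binomial(n, p):

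- Lead-in, n = 6, threshold 1: P(X ≥ 1) = 1 − (1 − p)^6. At p = 0.25 this is 82.2% (stated: more than 82%).
- Step 1, n = 30, threshold 6: P(X ≥ 6) = 79.7% at p = 0.25 (stated: more than 80%).

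Both reproduce to rounding.

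**4. Illustration of size.** The documents give no Grade 3 or Grade 4 rate, so each split below is an assumption. Suppose 25% of vaccinees have a laboratory value of Grade 3 or worse, and g points of that 25% are subjects whose only qualifying value is Grade 4. As written, the limb then works at p = 0.25 − g.

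| g | p counted | Lead-in, P(X ≥ 1) | Step 1, P(X ≥ 6) |
|---|---|---|---|
| 0 (or all count) | 0.25 | 82.2% | 79.7% |
| 1 point | 0.24 | 80.7% | 76.0% |
| 2 points | 0.23 | 79.2% | 71.9% |
| 5 points | 0.20 | 73.8% | 57.2% |

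At a lower assumed burden, 10% Grade 3 plus 1% Grade 4 only, the chance of meeting the limb goes from 46.9% (p = 0.10) to 50.3% (p = 0.11) per lead-in group, and from 7.3% to 10.5% in Step 1.

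**5. Sampling window.** The limb covers Days 1 to 7 after vaccination. The scheduled safety samples are drawn on Day 8 and Day 68 (Section 8.5.7, Table 25), at allowed intervals of 7 to 8 or 7 to 9 days after the dose (Tables 5 and 6). Read literally, those samples fall outside the window. The counts above assume that they are meant to be inside it.

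**The case against.** The strongest reply is that Grade 4 may have been meant to sit above rule 2. The scale calls it potentially life-threatening, every Grade 4 value is an SAE, and rule 1a needs one life-threatening SAE in any step. Grade 3 to 2c and Grade 4 to 1a would be a coherent scheme, and stricter than moving Grade 4 into 2c. The definition in 12.5.2 cuts against this reading without excluding it. What stands is that any fix must not make Grade 4 look as though it needs 6 of 30 in Step 1.

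A second reply is that crossing the threshold changes little. Section 8.6.2 sends a safety signal and a met rule 2 down the same path, to an iSRC decision on whether to hold; a met 2c is not an automatic hold. In Groups 1 to 3 the unblinded review on which 2c is assessed is itself conditional (8.6.5, 8.6.6). This stands and limits the consequence.

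Third, the window: if Days 1 to 7 is read as strictly as Grade 3, the scheduled samples drop out and a change of grade alone does little. This also stands, so the fix has to address both.

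Fourth, the larger effects above need high Grade 4 rates in subjects whose pre-vaccination values, where tested, had to be normal or non-significant Grade 1. At 5%, the chance of at least one Grade 4 subject among 30 vaccinees is 1 − 0.95^30 = 78.5%, and each would be an SAE reported within 24 hours (12.5.9.2). That is fair; those rows are illustrations only.

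A reader might infer that the figures in 8.6.4 are wrong. The documents do not support that. The figures give the chance that a rule is met at a given incidence of the event that rule counts, and they reproduce. They make no statement about laboratory toxicity of Grade 3 or worse.

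**Conclusion.** The point holds as a gap in wording. The laboratory limb of 2c leaves out the worst grade of its own scale, and no other formal rule clearly picks up a Grade 4 value without actual risk of death. The ordering fault is certain on the text. Its practical size is unknown because no grade rates are given, and it is small if Grade 4 values are rare.

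The consequence is confined to the formal threshold in the lead-in and PoP Step 1. A reader might infer that severe laboratory toxicity could pass unreported or could not lead to a hold. The documents say otherwise: Grade 4 values are expedited SAEs, Day 8 laboratory data are evaluated at each lead-in substep and before Step 2 (8.6.1), and the iSRC can hold on any safety signal (8.6.2).

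The conclusion assumes that the scheduled Day 8 and Day 68 samples are meant to count. The iSRC Charter, to which the protocol defers for details of the committees' evaluation, is not among the documents and might already settle the matter. The change is worth making while the affected steps are open or if the rule is reused.

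**What to change.** In Table 26, rule 2c:

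- change the laboratory limb to 'any Grade 3 or higher abnormality';
- state that the limb includes the scheduled Day 8 and Day 68 samples;
- add that this does not limit rule 1a for a Grade 4 value judged life-threatening.

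In Section 8.6.3, except Grade 4 laboratory abnormalities from the sentence on non-life-threatening SAEs.

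The cost is a few phrases, with no extra tests or visits. The downside is that 2c may be met slightly more often: at the assumed 10% Grade 3 and 1% Grade 4, about 3 percentage points more (50.3 − 46.9 = 3.4 per lead-in group, 10.5 − 7.3 = 3.2 in Step 1).
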